# 3.8 Study Endpoints

# 3.8.1 Primary end-point

Treatment engagement is the primary endpoint in this study.

- Confirmation of enrollment in MAT: Assessments will collect self-report of participation in MAT at the time
  of assessment as well as during the intervening time-period. We will also collect confirmatory
  documentation from the identified treatment provider. Permission to contact the treatment provider will be
  included in the consent and a specific release of information form signed by the participant will be included
  in the request for confirmation.
- CARES Integrated Data Systems Service Utilization: Participants enrolled in this study will provide consent to allow the Health Department to review their records of utilization of city services prior to and following enrollment in the study.

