## 4.8.2 Participant Education and the Informed Consent Process

Potential participants who express interest in initiating treatment will be engaged in a structured approach to education about the study and its procedures. The information delivered at this point will be supportive and motivational and describe study participation as an opportunity to consider options for treatment. It will also be explained that their participation can contribute to a better understanding of the most effective ways to assist individuals who want to begin treatment. Staff will make it clear that even if they do not become engaged in treatment, their experiences are important and their contributions to the research will be valuable. We will inform participants that their direct involvement in the project will last for one year and that we will want to contact them at scheduled assessment visits regardless of their treatment status. This discussion will offer potential participants a chance to ask questions and receive prepared materials explaining the study and the requirements for participation.

Those who appear to be eligible and express interest will begin the informed consent process to allow for screening. The informed consent process will give the participant an accurate understanding of the research procedures and make it clear that participation is voluntary. The informed consent document will be read and reviewed with the participant. The consent form includes clear language with special attention to the provision of permissions to contact the participant and individuals they identify as acceptable contacts if we are unable to make direct contact with the participant for the 1- and 6-month assessments. Since we will also need to confirm subsequent treatment engagement, the consent form will include permission to contact treatment providers to determine treatment status as well as permission for the Philadelphia Department of Public Health to look shared information about their subsequent use of health department services (CARES database. http://www.phila.gov/hhs/data/Pages/Cares.aspx). The consent form will also include a statement indicating that research staff will submit their names to the National Death Index for a record search should we be unable to make contact for a 90-day period.

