# 5.2 Sample Size and Power Determination

Our power analysis has been based on this primary aim. Our primary hypothesis is that participants who received rapid induction will more likely be engaged in ongoing treatment at 1- and 6-month follow-up than participants who sought treatment at BAC/CRC. We will test this hypothesis at a 5% level of significance. Our principal interest is in the comparison of engagement rates between the mobile intervention and BAC/CRC groups, at months 1 and 6. Preliminary data suggest an engagement rate of about 20-30% in the BAC/CRC group. Assuming a steady loss to attrition that yields 80% completers, and a within-subject correlation of 0.3, the methods of Diggle et al. (Diggle, Heagerty et al. 2002) show that our sample size of 125 in each group yields 80% power for differences of about 15% in engagement rates between the two groups (e.g., 80% power for BAC/CRC: 25% vs. Mobile: 40%, corresponding to a RR=1.6 and an OR=2.0)

**Propensity score model to account for non-randomized allocation:** The participants are not randomly assigned to the mobile rapid induction intervention and BAC/CRC groups, so it is possible that there will be confounding of the group effect with the effects of characteristics of the participants. We will use a propensity score approach (Rosenbaum 2002, Rothman, Greenland et al. 2008) to account for this. We will use a broad range of baseline variables as covariates in a logistic regression model predicting treatment group, including age, race/ethnicity, gender, number of previous overdoses, number of previous treatments for opiate use disorder, type of opioid used, and depression. The model will yield predicted probabilities of BAC/CRC group for all participants (the propensity score), and we will create a five-level ordinal variable based on the quintiles of the propensity score. We will then include this ordinal variable as a stratum variable in our models.

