**Analyses for the primary aim:** i.e. to evaluate the impact of the mobile, transitional MAT intervention on its ability to engage participants in targeted, existing MAT treatment slots at 1- and 6-month post-enrollment. For each of the 1- and 6-month time points, we will classify participants as being engaged/not-engaged (where non-engaged will include dropped out or missing). We will compare the groups on engagement rates at the two time points using a repeated measures logistic regression model, incorporating the propensity score as described above (Diggle, Heagerty et al. 2002). The fixed effects will be binary indicators of treatment group and time point; we will test for a group by time interaction to assess whether the group effect differs at month 1 and month 6. As there are only two time points, we will use an unstructured covariance matrix to accommodate within-participant covariance.

**Analyses for Aim 2:** We will also use a repeated measures model to compare the groups on the ASI drug composite score at months 1 and 6. The model will be similar to that described for the engagement analyses of Aim 1, but with a beta distribution assumed for the response, to accommodate the bounded range (zero to one) of the ASI composite scores. We will compare the groups on the number of overdoses per patient using repeated measures Poisson regression models, if there is sufficient variability in the number of overdoses reported. If a low rate of overdoses causes convergence issues for the Poisson model, we will classify participants as having no overdoses versus at least one, and compare the groups using repeated measures logistic regression models.

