**Missing data.** For the longitudinal analyses described above, premature discontinuation from treatment and occasional missing daily use indicators will lead to incomplete data. The repeated measures models described above can make use of all available data provided by subjects, but the inferences drawn from them will be unaffected by the missing data only if the missing data can be regarded as ignorable, essentially meaning that missingness can be predicted/explained from the baseline data and from responses obtained prior to drop-out. We will assess the sensitivity of our main analyses to the presence of missing data by performing a sensitivity analysis, in which we will obtain estimates of the group effect under various non-ignorability assumptions. We will use selection models to examine the effects of missing data (Robins, Rotnitzky et al. 1995), in which we will explicitly model the probability of premature discontinuation at a time point as a function of baseline characteristics and responses at previous time points, using logistic regression models, and incorporate the predicted probabilities into a weighted analysis of the main hypotheses.

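### The promised non-ignorable sensitivity analysis is, as described, a missing-at-random weighting that omits MAT status at the missed visit and does not clearly cover the Aim 2 ASI score.

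*Combined protocol and SAP*

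**What the plan says.** The Aim 2 paragraph of section 5.2 compares the groups on the ASI drug composite at months 1 and 6 with a repeated-measures beta model built like the Aim 1 model. It gives no rule for a score that was never collected.

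The *Missing data* paragraph supplies the general rule: "The repeated measures models described above can make use of all available data provided by subjects". The same sentence limits this to ignorable missingness, meaning missingness explained by baseline data and by responses before dropout. The plan then undertakes to re-estimate the group effect under several non-ignorable mechanisms. The technique offered models the probability of premature discontinuation "as a function of baseline characteristics and responses at previous time points" and uses the fitted probabilities as weights. It is directed at the main analyses and main hypotheses; the ASI score is not named.

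For Aim 1 the rule differs. Each participant is engaged or not at each visit, "where non-engaged will include dropped out or missing".

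Treatment status also has sources outside the interview. Section 3.8.1 plans confirmation from the treatment provider and consent for the Health Department to "review their records of utilization of city services prior to and following enrollment in the study". Section 4.8.2 says that "the consent form will include permission to contact treatment providers to determine treatment status".

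**The concern.** An ASI score exists only for people who are interviewed. The trial's premise is that being in MAT lowers drug use. If people who leave treatment are harder to find at month 6, the interviewed sample over-represents people in treatment, and the contrast describes drug use among those who could be found rather than among those enrolled.

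The *Missing data* paragraph itself names early discontinuation of treatment as a source of incomplete data, so this mechanism is one that the plan foresees. Its remedy does not reach it. Weights built from baseline and earlier responses correct only for missingness that those variables explain, which is the ignorable case again. At month 1 there is no earlier post-baseline response, so the weights rest on baseline alone. The quantity modelled is discontinuation, not absence of an ASI score. Nothing in the method expresses a departure from ignorability.

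The Aim 1 endpoint has no missing values once missing is coded as not engaged, so the ASI model is where a missing-data method is most needed. It is also the only drug-use outcome with a specified model: urine screens are collected (section 3.7), but no analysis of them is given.

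**Working it through.** **Plan's own figure.** Section 5.2: "We will test this hypothesis at a 5% level of significance"; "our sample size of 125 in each group yields 80% power for differences of about 15% in engagement rates between the two groups"; "80% power for BAC/CRC: 25% vs. Mobile: 40%, corresponding to a RR=1.6 and an OR=2.0". It also assumes 80% completers and a within-subject correlation of 0.3.

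- One time point, two-sided 5%, 80% power, 25% vs 40%: [1.96·√(2·0.325·0.675) + 0.8416·√(0.25·0.75 + 0.40·0.60)]² / 0.15² = 151.9, so 152 per group.
- Two repeated measures: 151.9 × (1 + 0.3)/2 = 98.7. Allowing for 80% completers: 98.7/0.8 = 123.4, against 125 stated.
- Power with 100 completers per group is 80.5%. RR = 0.40/0.25 = 1.6; OR = (0.40/0.60)/(0.25/0.75) = 2.0.

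The figure reproduces, so 25% and 40% are used below.

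**Inputs.** Month-6 follow-up is 90% in section 3.7 and 80% (completers) in section 5.2. Neither is given by group. The documents give no ASI mean or SD and no ASI difference between engaged and non-engaged people; call that difference d.

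**Formula.** If ASI differs between groups only through engagement, the contrast in everyone enrolled is (0.40 - 0.25)d = 0.15d. If every missed person is out of treatment, the contrast among those interviewed is (0.40/f_M - 0.25/f_T)d, where f_M and f_T are follow-up in the mobile and treatment-as-usual (TAU) groups.

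| Follow-up, mobile / TAU | Engaged among interviewed | Contrast | Change from 0.15d |
|---|---|---|---|
| 90% / 90% | 44.4% / 27.8% | 0.1667d | +11.1% |
| 80% / 80% | 50.0% / 31.3% | 0.1875d | +25.0% |
| 90% / 80% | 44.4% / 31.3% | 0.1319d | -12.0% |
| 80% / 90% | 50.0% / 27.8% | 0.2222d | +48.1% |
| 95% / 85% | 42.1% / 29.4% | 0.1269d | -15.4% |
| 85% / 95% | 47.1% / 26.3% | 0.2074d | +38.3% |

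**Weaker assumptions about the missed people.**

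- They engage at half the rate of those seen: the ratio is 1/(f + (1 - f)/2), which gives +5.3% at 90% and +11.1% at 80% follow-up.
- The same share of the non-engaged is missed in each group: +5.2% with 10% missing overall, +10.0% with 20%.
- They engage at the same rate as those seen: 0%.

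**Does month-1 ASI rescue the model?** In a simulation of 400,000 per group, missing was 5%/10% or 10%/20% at months 1/6, equal between groups and confined to the non-engaged. The engagement correlation was 0.3; mean ASI was set at 0.10 engaged and 0.30 non-engaged, with SD 0.05 or 0.12 (all assumed). A normal likelihood fit to all available data gave a month-6 bias of about +10% and +23%. Averaged over both visits it was about +8% and +17%. Earlier ASI data remove little of the bias.

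**Logit scale**, closer to the beta model: with assumed ASI means of 0.05-0.20 engaged and 0.25-0.35 non-engaged, the 90% and 80% rows become +12 to +15% and +27 to +35%.

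**Absolute size**, assuming d = 0.15 and SD 0.12 within engagement status:

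- 90% / 90%: bias 0.15 × 0.0167 = 0.0025. The variances are 0.12² + 0.15²·q(1 - q) = 0.0200 and 0.0189 for q = 0.444 and 0.278, so SE = √((0.0200 + 0.0189)/112.5) = 0.0186. Bias is 0.13 SE.
- 80% / 80%: bias 0.15 × 0.0375 = 0.0056; SE = √((0.0200 + 0.0192)/100) = 0.0198. Bias is 0.28 SE.
- 80% / 90%: bias 0.15 × 0.0722 = 0.0108; SE = √(0.0200/100 + 0.0189/112.5) = 0.0192. Bias is 0.56 SE.

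**The case against.** The plan is not naive about this. It states the ignorability condition and announces non-ignorable scenarios, so a reader who infers that it simply assumes missing people to be ignorable goes too far. That stands.

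A reader might also infer that the Aim 1 coding and the Aim 2 model contradict each other. They do not. Coding missing as not engaged is a convention for one binary endpoint, not a statement about where those people are, and it can coexist with an available-data model for another outcome.

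Nor is imputing ASI from the Aim 1 coding a safe new main analysis. If missed people engage at the same rate as those seen, the available-data contrast is right at 0.15d. Coding them all as non-engaged would give 0.80 × 0.15d = 0.12d (-20%) at 80% follow-up and 0.90 × 0.15d = 0.135d (-10%) at 90%. This also stands.

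Records have limits. Provider confirmation needs an identified provider and a signed release (section 3.8.1). CARES is used with the participant's permission and covers services that the City provides (section 3.2). The mobile group's case manager arranges the provider, while TAU study staff only assess (section 4.9.1), so ascertainment may differ by group. And if records show some missed people in treatment, the table's all-out-of-treatment assumption fails.

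Finally, under equal follow-up the absolute bias is small against the standard error. Unequal follow-up is conceivable, since the mobile group has frequent team contact, but TAU has its own follow-up assistants and section 3.7 gives one expectation for the whole study.

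These points limit the size of the claim and the remedy. None of them supplies the non-ignorable analysis that the plan promises.

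**Conclusion.** The gap is real and lies in the text. The plan makes the ASI result conditional on ignorability and promises to test that condition. It then describes a weighting that relies on the same condition, omits MAT status at the missed visit, and is not stated to apply to the ASI score.

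A reader might infer that the ASI effect is biased by a fixed amount, roughly 10% to 25%. The documents do not support that. Those values need equal follow-up, every missed person out of treatment, and ASI driven by engagement alone, and the plan states none of the three. Under unequal follow-up the same arithmetic runs from about -12% to +48% (a 95%/85% split reaches -15%). If missed people resemble those seen, the bias is zero. Because neither size nor sign can be known in advance, the sensitivity analysis should be fully specified. The main model need not be replaced.

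**What to change.** In *Missing data* and *Analyses for Aim 2*:

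1. Keep the available-data model as the main ASI analysis, and state that the sensitivity analysis covers the ASI drug composite.
2. Model having an ASI score at each visit, or multiply impute the score within group. Use documented MAT status at that visit (provider confirmation or CARES), baseline ASI, the propensity covariates and any observed ASI score.
3. Where records give no status, treat it as unknown, not as non-engaged. Show results with unknowns taken as non-engaged and with unknowns taken to engage at the same rate as those seen.
4. Add a delta-adjusted analysis: shift the imputed scores by a stated range, separately by group and on the logit scale so that they stay within bounds, and report where the conclusion changes. This delivers the promised non-ignorable scenarios.
5. Do not impute ASI scores after death. Report deaths, ASI follow-up and MAT-status ascertainment by group.

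The cost is plan wording, some programming and slightly wider intervals. No new visits are needed, since the record sources are already planned under consent. The remaining weakness is reliance on record completeness, which may differ between groups; item 5 makes that visible.

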# 1 Study Summary

Title	Rapid initiation of buprenorphine/naloxone to optimize MAT utilization in Philadelphia		
Short Title	Rapid initiation of BUP/NX		
Study overview	The proposed research will evaluate the ability of a mobile, rapid induction procedure to engage individuals in ongoing medication assisted treatment. A total of 250 untreated ndividuals meeting criteria for opioid use disorder and at high risk of opioid overdose will be enrolled in the study. Recruitment will take place in two targeted neighborhoods of Philadelphia (Kensington and South Philadelphia) with a high prevalence of fatal and non- fatal opioid overdose. A total of 250 participants will be engaged in the research. Following nformed consent and determination of eligibility, 125 individuals will be enrolled as they engage with the mobile, rapid induction team and 125 individuals will be enrolled as they seek treatment from the CRC Episcopal Hospital (serving Kensington area) or BAC/CRC Hall Mercer Community Mental Health (serving South Philadelphia). The intervention group will receive four weeks of treatment with buprenorphine /naloxone and support for treatment engagement provided by a case manager and a peer recovery specialist. All participants will be assessed at baseline and then 1- and 6-month following enrollment. The primary endpoint for the study is continued enrollment in medication-assisted treatment at 6 months post enrollment.		
Study Duration	The estimated duration of study is 36 months. Individual study subject participation will last 6 months.		
Study Center(s)	The University of Pennsylvania will serve as the primary project location, and all recruitment and data collection efforts will be executed by University of Pennsylvania staff members. A subcontract has been established with Prevention Point Philadelphia and Public Health Management Corporation.		

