	case manager and PRS will work with the participants to belo them become engaged					
	in existing medication assisted treatment programs					
	• The type of ongoing treatment will be determined on an individual basis and will					
	include options of methadone maintenance, buprenorphine/naloxone treatment, or					
	extended-release naltrexone (XR-NTX).					
	Comparison on engagement rates in ongoing opiate use disorder treatment at the					
	two time points (1- and 6-months) using a repeated measures logistic regression					
	model, incorporating the propensity score (to correct for non-randomized trial)					
	Evaluate the change in substance use and severity of addiction using a repeated					
	measures model to compare the groups on the ASI drug composite score at months					
	1 and 6.					
Statistical	Compare of the number of overdoses per participant between groups using repeated					
Mothodology	measures Poisson regression models, if there is sufficient variability in the number of					
wethodology	Poisson model, we will classify participants as baying no overdoses versus at least					
	one and compare the groups using repeated measures logistic regression models					
	
 
Evaluation of the sensitivity of our main analyses to the presence of missing data by
 
					
	performing a sensitivity analysis, in which we will obtain estimates of the group effect					
	under various non-ignorability assumptions, using selection models to examine the					
	effects of missing data, using logistic regression models, and incorporate the					
	predicted probabilities into a weighted analysis of the main hypotheses.					
	The study will be monitored by the PIs and co-investigators, and Philadelphia Department					
Data and Safat	of Public Health Institutional Review Board, as well as by regulatory committees at the					
Data and Salety	University of Pennsylvania (i.e., IRBs, OHR) and Center for Studies of Addiction Data Safety					
Monitoring Plan	Monitoring Board (Penn DSMB). During the course of the study, safety and data quality					
	monitoring will be performed on an ongoing basis by the Principal Investigator and the study					
	staff.					

The information that follows constitutes the research protocol for the Rapid initiation of buprenorphine/naloxone to

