The mobile team's Case Management (CM) function will be performed by a master's level social worker. The CM will have primary responsibility for identifying the treatment program that best meets the needs of the participant. The CM effort will be sharply focused on identifying and removing barriers to MAT treatment engagement. This will include completing medication authorization forms and insurance enrollment if necessary, and then making referrals to additional supports, including mental health treatment, housing, medical, legal support, and peer-based recovery supports in the community. The CM will work collaboratively with participants to remove barriers to care and to enhance program outcomes and to provide psychosocial support.

The mobile team will insure that there is a clear plan for rapid engagement with ongoing treatment as soon as possible. Buprenorphine/naloxone will be provided during the time of transition to their long-term provider for up to 1 month. Telephone support will be available should participants have questions or need assistance and the mobile team will also have daily contact with participants until they complete contact with their ongoing provider.

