## Comparison group – Treatment as usual

During the same period of time, participants will also be recruited at the City of Philadelphia Behavioral Health System Behavioral Assessment Centers (BAC) and Crisis Response Centers (CRC) located at Episcopal Hospital serving Kensington area and Hall Mercer BAC/CRC (a University of Pennsylvania program) serving South Philadelphia area. Two research assistants from the TRI-PHMC will enroll and follow-up 125 participants at BAC/CRC. The participants will complete the same assessments at baseline, 1- and 6-month follow-up. Authorization for the Philadelphia Department of Public Health to look shared information about their subsequent use of health department services (CARES database, http://www.phila.gov/hhs/data/Pages/Cares.aspx) will also be requested in the consent form. Research staff will only conduct assessments. Treatment engagement services will be provided by the staff of the BAC/CRC as usual.

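### The missing-data plan promises non-ignorable estimates, but the only model it specifies is missing-at-random weighting, and it does not say how that weighting treats engagement already coded as not engaged

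*Combined protocol and SAP*

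**What the plan says.** The Missing data paragraph is printed under section 5.2; the contents list places statistical methods at 5.3. It says the repeated-measures models are unaffected by missing data only if missingness is ignorable, "essentially meaning that missingness can be predicted/explained from the baseline data and from responses obtained prior to drop-out". It then promises a sensitivity analysis "in which we will obtain estimates of the group effect under various non-ignorability assumptions". The method that follows is called a selection model. It will "explicitly model the probability of premature discontinuation at a time point as a function of baseline characteristics and responses at previous time points", by logistic regression, and the predicted probabilities will weight an analysis of the main hypotheses. The Statistical Methodology entry of the Study Summary joins promise and method in one sentence ("under various non-ignorability assumptions, using selection models to examine the" effects of missing data) and names no further model.

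For the primary aim, the same part of section 5 classifies each participant at months 1 and 6 as engaged or not, "where non-engaged will include dropped out or missing". Section 3.8.1 adds provider confirmation and city service (CARES) records as sources of engagement status, but no rule says when a participant who missed a visit still counts as missing.

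**The concern.** A missing-data model is non-ignorable only if missingness may depend on the unseen value after allowing for what was seen. The model described has no such term and no sensitivity parameter. If the weighted estimate came out close to the main one, it could be reported as robustness to non-ignorable dropout, although that possibility had not been examined.

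The gap matters most for engagement. Coding all unresolved participants as not engaged is itself a strong assumption, and the group comparison depends on whether it is equally wrong in both arms. The study is non-randomized and open-label, and follow-up is organized differently by arm. In usual care, "Two research assistants from the TRI-PHMC will enroll and follow-up 125 participants at BAC/CRC". In the mobile arm, "the mobile team will also have daily contact with participants until they complete contact with their ongoing provider". If engaged usual-care participants are missed more often than engaged mobile participants, the coding inflates the mobile effect, and nothing specified would show it.

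**Working it through.** **Step 1. Compare definition and model.** Ignorable, by the plan's definition: missingness explained by (a) baseline data and (b) responses before drop-out. Model specified: discontinuation predicted from (a) baseline characteristics and (b) responses at previous time points. The inputs are the same. The current unseen response appears in neither, and no delta, pattern-mixture or tipping-point element is given. The specified analysis is therefore MAR.

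**Step 2. Engagement.** With missing coded as not engaged, every participant has a value at both visits, so no observation is left for the weights to correct. Undoing the coding and weighting the observed values would give an estimate, but still a MAR one.

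**Step 3. Reproduce the plan's power figure.** Section 5.2: 125 per group, 80% completers, two visits, correlation 0.3, 25% vs 40%, 5% level (two-sided assumed). Effective n per group = 100 × 2 / (1 + 0.3) = 153.8. A pooled two-proportion test then has 80.5% power, against 80% stated. The inputs are understood as intended.

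**Step 4. How far engagement depends on the unseen.** This is an approximation to the planned model, without propensity strata. Let a and b be the engaged counts (mobile, usual care) out of 125 at each visit:

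- d = [(a1 − b1) + (a6 − b6)] / 250
- at each visit, q = (a + b)/250 and v = q(1 − q) × 2/125
- SE = √[(v1 + v6 + 2 × 0.3 × √(v1·v6)) / 4], z = d/SE

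*Scenario A: 40% vs 25% among those seen, 90% then 80% seen (steady loss assumed).* Counts are 45 vs 28 and 40 vs 25. d = (17 + 15)/250 = 0.128, SE = 0.0456, z = 2.81, p = 0.005. Now let some unseen usual-care participants, and no unseen mobile participants, be engaged:

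| Added in usual care | d | p |
|---|---|---|
| 9 of 25 at month 6 | 0.092 | 0.048 |
| 10 of 25 at month 6 | 0.088 | 0.059 |
| 3 at month 1 + 6 at month 6 | 0.092 | 0.048 |
| 3 at month 1 + 7 at month 6 | 0.088 | 0.059 |

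A logistic GEE (group and time, exchangeable) on constructed data with these counts gives 0.005 as coded, 0.049 for +9 and 0.060 for +10.

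*Scenario B: same rates, 95% then 90% seen (section 3.7).* Expected counts are 47.5 vs 29.7 and 45 vs 28.1; p = 0.003. Adding 11 of about 12 at month 6 gives 0.047. Adding 4 of about 6 at month 1 and 8 of about 12 at month 6 (integer counts 48 vs 34, 45 vs 36) gives 0.054.

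*Scenario C: 40% vs 25% are the rates after coding (50 vs 31 at both visits), 25 unseen per arm at month 6.* d = (19 + 19)/250 = 0.152, p = 0.001. Adding 14 gives 0.048; adding 15 of 25 gives 0.059.

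**Step 5. Month 6 alone.** The Study Summary says "The primary endpoint for the study is continued enrollment in medication-assisted treatment at 6 months post enrollment". Single-visit pooled z-test: z = [(a − b)/125] / √[q(1 − q) × 2/125].

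- Rates among those seen: 40 vs 25, p = 0.031; 40 vs 27 (2 added), p = 0.063.
- Rates as coded: 50 vs 31, p = 0.010; 50 vs 36 (5 added), p = 0.062.
- Equal engagement among the 25 unseen in each arm, from 0 to 40%, starting from 40 vs 25: p moves only from 0.031 to 0.045. The contrast between arms is what matters.

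**Step 6. What the weighting does under each mechanism.** Simulation with assumed parameters, 300,000 participants, about 32% engaged in both arms (true difference −0.2 points). With dropout driven by baseline, arm and earlier response, weighting recovers −0.2. With dropout also driven by unseen month-6 status, differently by arm (86.7% vs 80.2% retained), weighting gives 5.3 points, the same as the unweighted observed cases; missing coded as not engaged gives 6.4.

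**The case against.** **An alternative for engagement may be implied.** A reader might infer that the plan offers nothing besides missing means not engaged. The documents do not support that. The weighting is meant for the main hypotheses, the primary hypothesis is engagement, and the models are said to use all available data. A weighted analysis of observed engagement is a fair reading. What stands is narrower: the plan does not say the coding is undone, and that analysis would still be MAR.

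**The result may be sturdier than month 6 suggests.** A reader might infer that two hidden engaged usual-care participants would overturn the trial. That figure comes from an unadjusted single-visit test and takes 40% vs 25% as rates among those seen. The planned model uses both visits, and the same reading then needs 10. If unseen usual-care participants were engaged at the 25% rate (3 of about 12 at month 1, 6 of 25 at month 6) and no unseen mobile participant was, p would still be 0.048. This objection stands on size, and the two-visit figures should lead.

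**Differential ascertainment is not shown.** A reader might infer that usual care is followed less well. Sections 4.9 and 4.9.1 give both arms research assistants and the same assessments. The mobile team's contact falls within support of up to one month and says little about month 6. Differential ascertainment is possible, no more. The calculations also assume equal missingness in both arms.

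**Several methods would serve.** Tipping-point and delta-adjusted analyses are not the only valid choices. True, but the plan must name at least one that can do what it promises.

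**Conclusion.** The mismatch between promise and method is established from the text alone: by the plan's own definition, the one model it specifies is an ignorable-missingness model. For the primary outcome there is also an ambiguity about whether missing engagement is recoded before weighting; neither answer gives a non-ignorable estimate.

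The effect on the conclusion depends on assumptions the documents do not settle. In the two-visit approximation, losing significance takes 10 of 25 usual-care-only additions at month 6 (Scenario A), nearly all of the unseen or a spread such as 4 plus 8 (Scenario B), or 15 of 25 (Scenario C). Month 6 alone takes 2 or 5. These figures treat every unseen participant as unresolved, which is an upper bound because provider and CARES records may settle some, and they leave out propensity strata. They do not show that the primary result would be overturned or that the primary test is invalid. They show that the answer depends on the missingness pattern, which the specified sensitivity analysis cannot reveal. This should be corrected before outcome data are examined.

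**What to change.** 1. **Engagement.** State that provider confirmation and CARES records are used first to resolve status. For those still unresolved, add a tipping-point analysis within the planned two-visit model, with propensity strata. Take not engaged in both arms as the reference, vary the engagement probability separately by arm, and report where the conclusion changes.
2. **Weighting.** Label it a MAR analysis. State either that for engagement it uses observed status only, with the coding undone, or that it is not applied to engagement. Model missed assessment instead of treatment discontinuation, since section 4.10 continues follow-up after the intervention stops.
3. **ASI and overdose.** These outcomes can be truly missing, so the MAR weighting has a proper role. Add one explicit missing-not-at-random analysis with an arm-specific sensitivity parameter, for example delta-adjusted imputation, or withdraw the non-ignorability claim for these outcomes.
4. **Study Summary.** Amend the Statistical Methodology entry to match.

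The cost is revised wording and modest extra programming. No new data, visits or participants are needed.
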